### 8.1.5 Week 30 Follow-up visit

1. For post menarcheal females, collect a urine sample and perform a urine pregnancy test.
2. Record the % BSA involved by psoriasis (excluding face and scalp) (See section 13.3, Appendix 3).
3. Obtain serum samples for laboratory testing (full panel) for subjects in the PK group. For all other subjects, obtain serum samples for laboratory testing at the Investigator's discretion (all subjects). Obtain urine for urinalysis (all subjects).
4. Obtain serum samples for 1,25(OH)2D, 25(OH)D and serum PD parameters for subjects in the PK group. For all other subjects, obtain serum samples at the Investigator's discretion. Prepare them according to the Central Laboratory manual.
5. Obtain 24-hour urine sample for PD urine for subjects in the PK group and send it to the central lab for analysis. For all other subjects, obtain 24-hour urine sample at the Investigator's discretion and send it to the central lab for analysis.
6. For selected subjects enrolled in the PK analysis: Collect blood sample for PK assessment.
7. Evaluate IGA.
8. Evaluate pruritus.
9. Question the subject's parent/legal guardian or subject (according to subject's maturity level) about the occurrence of Adverse Events. Non-persuasive open ended questions are to be asked, such as "Have you noticed any change in your health since last visit?"
10. Question the subject's parent / legal guardian or subject (according to subject's maturity level) specifically about symptoms of kidney stones e.g. obvious hematuria or pyuria, or vague abdominal or flank pain/ discomfort, or possible pain radiating to the groin area.
11. Ask the subject and parent/legal guardian whether there have been any changes to his/her concomitant therapies/procedures (added, removed, or changed) since the previous visit. Document all changes on the Drugs/Therapies form in the eCRF.
12. After collecting all data from the subject (including laboratory samples results), complete the Exit form of the eCRF.

### **8.1.6      **Unscheduled visits****

When necessary and exceptionally, unscheduled visits could take place due to an advent event (AE) needing a specific treatment, AE leading to withdrawal from the study, laboratory result(s) that warrant further testing, or other reason. Please complete appropriate eCRF AE form if necessary. Assessments to be performed will be at the Investigator's discretion according to the reason for the Unscheduled visit.

### **8.2      **Subject instructions (other than study drug(s) administration)****

Subjects should wait at least six hours after the study treatment application before swimming or bathing.

The Cetaphil® Moisturizing Cream or equivalent (provided by the Sponsor) may be used during the study as needed on non- treated areas of the skin. A Cetaphil® Gentle Skin Cleanser or equivalent (provided by the Sponsor) may be used for cleansing.

Subjects will be permitted to use medicated shampoos that do not contain corticosteroids or vitamin D derivatives to treat scalp psoriasis. Tar products can be used on the face and scalp areas.

No other topical treatments, other than the test materials, will be permitted on the treated areas. However, emollients and sunscreen on healthy skin areas are permitted during the course of the study.

Dietary instructions: subjects will be asked to maintain the same dietary habits, especially calcium intake as before the study. Subjects should maintain adequate hydration. Detailed instructions will be provided to the subjects regarding appropriate hydration in the subject instructions document.

It is recommended that the subject use protective clothing and other measures/precautions to protect themselves from excessive sun exposure while participating in this study.

## 9 STATISTICAL METHODS PLANNED

### 9.1 Statistical and analytical plans

A Statistical Analysis Plan (SAP) will be developed as a separate document. The SAP will contain a more detailed and technical description of specific data conventions, calculations and of statistical procedures for executing the analyses that are specified in the sections of the clinical trial protocol below. Any change to the primary objective of the study or to the statistical method of primary endpoint will require the protocol and the SAP to be amended prior to database lock. Changes to the planned analyses of other non-primary endpoints, as well as any additional and unplanned statistical analyses will be documented in the clinical study report, and in an amended SAP if these changes occur before database lock. Any further change to the planned analyses (such as, addition of post-hoc analyses) made to the finalized SAP will be documented in the clinical trial report.

#### 9.1.1 Analysis Endpoints

##### 9.1.1.1 *Efficacy Endpoints*

- Percentage of subjects with an IGA Score of 0 (clear) or 1 (almost clear).
- Change from Baseline in Pruritus
- Change from Baseline in % BSA

##### 9.1.1.2 *Key Safety Endpoints*

- Laboratory: Serum albumin-adjusted calcium, urine calcium : creatinine ratio, phosphorus, and PTH.
- Adverse Events

##### 9.1.1.3 *Pharmacokinetic Endpoint*

- $C_t$

### **9.1.2 Populations analyzed, evaluability and limitation / evaluation of bias**

Prior to the final database lock of the study, a data review will occur to assess the potential bias of any data issues for final statistical analyses; and to determine the final subject populations for statistical analyses. Decisions made from the data review will be documented and any changes to the SAP will be made before database can be locked.

The statistical analyses will be performed based on the safety population.

#### **9.1.2.1 *Safety Population***

The Safety Population is defined as all subjects who have applied the study drug at least once.

### **9.1.3 Data presentation and graphics**

In general, the categorical variables will be summarized by frequency and percentage for each response category (N, %). The continuous variables will be summarized using means, medians, minimum, maximum, and standard deviations for the data collected at each visit

### **9.1.4 Efficacy analysis methods**

#### **9.1.4.1 *Handling of missing data***

No missing data handling will be performed. All data will be summarized as observed.

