## 3 OVERALL CLINICAL TRIAL DESCRIPTION

This is an open-label, uncontrolled, multicenter long-term safety and efficacy study in pediatric subjects (age 2-16 years and 11 months, Version R03) with mild to moderate plaque psoriasis.

Approximately one hundred (100) subjects will be enrolled into this study. A subset of enrolled subjects (approximately 9 among the 100) will meet the PK requirements: pediatric subjects aged 2 to 6 years and 11 months (inclusive at Screening) and with a minimum 3% BSA involvement.

Qualified subjects will receive calcitriol 3 mcg/g ointment for a period of up to 26 weeks. The subject's parent/legal guardian or the subject under the responsibility of the parent/legal guardian will apply a thin film of study drug as needed to cover all involved areas twice daily, without exceeding a maximum of 0.5 g/kg of body weight or 28 g daily (whichever is the lower). If the subject experiences complete clearing of psoriasis per physician assessment (i.e. an IGA of 0), the subject should discontinue the study drug but continue to follow the visit schedule through the Week 26 visit. Treatment with study drug should be resumed if the IGA score is >0 and <4.

Subjects will be evaluated at screening, baseline and Weeks 4, 12, 26, and 30 as described in the Schedule of Assessments (Table 2). A visit window of  $\pm 5$  days will be allowed for Baseline and a visit window of  $\pm 3$  days will be allowed at the visits from Weeks 4 through 30.

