## 5.6 Procedures/Reasons for subject discontinuation

An Investigator may decide to discontinue a subject from the clinical trial for safety reasons.

Although the importance of completing the entire clinical trial should be explained to the subject by the clinical trial personnel, any subject is free to discontinue his/her participation in this clinical trial at any time and for whatever reason, specified or unspecified, and without any prejudice. No constraints are to be imposed on the subject, and when appropriate, a subject may be treated with other conventional therapy when clinically indicated.

When a subject does not complete the clinical trial, he/she will be fully assessed, if such assessment is possible. The procedures designated for the Week 26/Early Termination visit should be completed for all subjects discontinuing the clinical trial and the appropriate Case Report Form eCRF should be completed. All discontinuations and the reason for discontinuation are to be documented by the Investigator on the Exit Form, and also on the Adverse Event Form for discontinuation due to an AE.

For discontinuation due to an AE, the Investigator should ensure that the subject receives suitable therapy for his/her AE.

Subjects who have a 2 grade worsening of their plaque psoriasis per the IGA scale, or who reach an IGA of 4, should be discontinued and complete the Week 26/ET visit. If the subject experiences complete clearing of psoriasis (IGA = 0), per physician assessment the subject should discontinue the study drug but continue to follow the visit schedule through the Week 26 visit. Treatment with study drug should be resumed if the IGA score is >0 and <4.

Subjects whose parathyroid hormone (PTH) results fall below the lower limit of normal will be assessed on a case-by-case basis; study drug application may be temporarily discontinued based on Sponsor and Investigator assessment. Serum PD parameters will be regularly checked (at least within 2 weeks) at Investigator's and Sponsor's discretion until the PTH level is back within the normal range. In addition, the IDMC will be notified of all PTH results that decrease by 30% from the subject's baseline results and will recommend appropriate management of the subject on a case-by-case basis.

For subjects whose parathyroid hormone (PTH) results have fallen below the lower limit of normal, if either:

- The PTH does not return to the normal reference range within two weeks

OR

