- The PTH returns to the normal reference range but falls below the lower limit of normal at any other stage during the course of the study

then the IDMC will be contacted for advice on management.

Subjects with abnormal serum albumin-adjusted calcium should temporarily discontinue study drug use immediately. The IDMC will be consulted for each occurrence of hypercalcemia, and depending on the severity and/or duration of the out-of-range serum calcium, will recommend appropriate management of the subject on a case-by-case basis in combination with other lab values and clinical condition of the subject in general.

Subjects with suspected kidney stones should temporarily discontinue study drug and will be referred to their Primary Care Physician (PCP) for care in tandem with Sponsor consultation of the IDMC. If urolithiasis is not confirmed, the subject may resume treatment with study drug. Subjects with confirmed urolithiasis should permanently discontinue study drug use and complete the Week 26/ET visit.

A subject who has been enrolled and assigned a kit number cannot be replaced by another subject if he/she discontinues the clinical trial for any reason.

For subjects not completing the entire study, all used (and unused) study drugs containers should be returned by the subject's parent/legal guardian to the defined personnel at the study center.

GALDERMA may also decide to prematurely terminate or suspend a subject's participation in the clinical trial.

Potential reasons for discontinuation, as listed on the Exit Form, are defined below:

- **Pregnancy:** **Withdraw the Subject from the clinical trial and follow the procedure described in Section 7.2.3.2.4**
- **Lack of Efficacy:** Investigator judgment only: based on therapeutic/disease-state expectations. If subject/parent or legal guardian opinion only, mark "subject request" and document it in the comment section of the eCRF Exit Form.
- **Adverse Event:** Complete an Adverse Event Form.
- **Subject Request:** Includes consent withdrawal, subject relocation, schedule conflicts. Explain the reason for withdrawal in the comment section of the eCRF Exit Form.
- **Protocol Violation:** Explain the violation in the comment section of the eCRF Exit Form.
- **Lost to Follow-up:** Confirmed with two documented phone calls and a certified letter (delivery receipt requested) without answer. Explain in the comment section of the eCRF Exit Form.

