7.2.5 Efficacy Analysis

No formal inferential statistical analysis will be performed. All efficacy data will be summarized as observed based on analysis visit as well as additional analysis visit of Week 26 (LOCF, last observation carried forward). (Section 7.5). Analysis visit of Week 26 (LOCF) will be assigned as the last available data (excluding unscheduled visit) during treatment period. If there is no data available post baseline, the baseline visit will be used.

IGA and pruritus will be summarized over time by each category and by shift change.

Observed and changes from baseline of the IGA, Pruritus, and Percent BSA over time will be summarized as continuous variables. Additionally, change from baseline in efficacy data over time will be presented graphically.

In addition, IGA, pruritus, and Percent BSA will be summarized descriptively by gender, race, and age group (2-5 years, 6-12 years, 13-17 years).

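### The as-observed Week 26 IGA 0/1 percentage leaves out early treatment failures, and no planned row counts leavers as non-responders

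*Protocol*

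**What the plan says.** **Protocol**

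- Section 9.1.1.1 lists the share of children with IGA 0 or 1 as an endpoint, without a time point or denominator.
- Section 9.1.2.1 sets the population: "The Safety Population is defined as all subjects who have applied the study drug at least once".
- Section 9.1.4.1 rules out any handling of missing data and adds: "All data will be summarized as observed".
- Sections 5.6 and 6.4 say that children who worsen by two IGA grades "or who reach an IGA of 4, should be discontinued and complete the Week 26/ET visit".
- Section 5.6 also allows exit for lack of efficacy: "Investigator judgment only: based on therapeutic/disease-state expectations".
- Clearing is handled differently. At IGA 0, "the subject should discontinue the study drug but continue to follow the visit schedule through the Week 26 visit" (Section 3).

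**SAP**

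- Sections 7.2.5 and 7.2.6.2 report efficacy as observed and add a further row: "Analysis visit of Week 26 (LOCF) will be assigned as the last available data (excluding unscheduled visit) during treatment period". Baseline is used when nothing later exists.
- Section 7.5, Table 2, assigns efficacy visits by study day. Week 12 is days 71 to 112, Week 20 is days 113 to 161 and Week 26 is days 162 to 196. When two values share a window, the one nearer the target day is kept. Unscheduled visits are not used for efficacy.
- Section 8 declares no departure from the protocol's analysis plan.

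**The concern.** Some of the data missing at Week 26 are missing because of the outcome. A child who gets much worse is taken off study by rule, and one who fails to improve may leave by judgment. If the Week 26 percentage is then computed only on children with a value in the Week 26 window, the poorest outcomes are under-represented.

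There is no control arm, so nothing offsets this selection and the percentage is read at face value. Long-term efficacy is in the title, the objectives and the clinical hypothesis. The same rows also feed the summaries by gender, race and age group, where a few leavers can move a percentage noticeably.

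The two documents also disagree on missing data. The protocol rules out any handling, while the SAP carries values forward and declares no change.

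**Working it through.** **1. Figures in the plan.** No response rate or dropout rate is stated. The only planning figure is the number screened: 100/(1 − 0.40) = 166.7, rounded up to 167. It reproduces but has no bearing here.

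**2. Where an early failure goes under the SAP.** Suppose a child has a scheduled visit on day 85 and an early-termination visit with IGA 4 on day 100. Both fall in days 71 to 112. Day 85 is 0 days from target and day 100 is 15 days from it, so day 85 is kept. The IGA 4 then appears in no as-observed row. With early termination on day 130, the value goes to the Week 20 row. In both cases the child is absent from the as-observed Week 26 row. In the LOCF row the last value is IGA 4, a non-response.

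**3. Formulas.** All inputs are assumptions:

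- d = share of treated children with no value in the Week 26 row
- p = IGA 0/1 share among those with a value
- q = share of leavers whose last treatment-period value was 0 or 1

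The three summaries are then:

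- As observed = p
- Leavers counted as non-responders (NRI) = p(1 − d)
- LOCF = p(1 − d) + qd

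So as observed − NRI = pd; LOCF − NRI = qd; LOCF − as observed = d(q − p).

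**4. As-observed minus NRI (pd), in percentage points**

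| d | p = 30% | p = 50% | p = 70% |
|---|---|---|---|
| 10% | 3 | 5 | 7 |
| 20% | 6 | 10 | 14 |
| 30% | 9 | 15 | 21 |
| 40% | 12 | 20 | 28 |

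**5. One case in full.** Take 100 treated, d = 20% and p = 50%. As observed is 40/80 = 50%. NRI is 40/100 = 40%. LOCF is 40% at q = 0, 45% at q = 0.25, 50% at q = 0.5 and 60% at q = 1.

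**6. The same case by nominal visit.** If the combined Week 26/ET visit were tabulated as one row, 10 early-termination failures would give 40/90 = 44.4%, and 20 would give 40/100 = 40%. The omission therefore comes from the study-day windows, or from an early-termination visit that was not done.

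**7. Against the true rate.** Let r be the response that leavers would have had at Week 26. The all-treated rate is p(1 − d) + rd, so as observed exceeds it by d(p − r). In the case above that is 10 points at r = 0, 5 at r = 0.25 and 0 at r = 0.5. LOCF exceeds it by d(q − r), which can have either sign.

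**The case against.** The strongest reply is that neither document, read alone, leaves IGA 4 exits out of every Week 26 figure. In the protocol's Table 2, Week 26 and early termination are one visit, discontinuing children are asked to complete it, and there are no study-day windows. Windows exist only in the SAP, and the SAP adds the LOCF row that brings those children back. This stands, and it places the problem in the SAP's as-observed row. It does not remove it: the protocol does not say how the combined visit is tabulated, and the document that does say files it by study day.

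The LOCF row also deserves credit. It keeps every treated child. With no later data it uses baseline, where IGA is 2 or 3 by eligibility, so the child is a non-responder. It exceeds the as-observed figure only if q > p.

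A reader might infer that LOCF mainly credits children who cleared, stopped the drug and drifted away. The documents do not support that. Cleared children are told to keep attending, and clearing is not among the exit reasons in Section 5.6. The credit goes only to children who leave, or miss Week 26, with a last value of 0 or 1. If no early-termination visit is done, the carried value under the current visit schedule is 26 − 12 = 14 or 26 − 4 = 22 weeks old.

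Finally, protocol Section 9.1 allows additional non-primary analyses if they are documented, and the SAP tabulates discontinuation by reason and by visit. A careful reader could divide the Week 26 responder count by the Safety Population and obtain the missing figure. That also stands, and it is why this is a small point.

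**Conclusion.** The point holds in limited form. The as-observed Week 26 row omits children who fail and leave before day 162, and some of those failures can be absent from every as-observed row. LOCF repairs that but credits leavers whose last value was 0 or 1. No planned row counts leavers as non-responders.

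Relative to such a row, as observed is higher by pd, which is 3 to 28 points for d of 10 to 40% and p of 30 to 70%. LOCF is higher by qd, which is zero if no leaver exits at 0 or 1. All of d, p and q are assumptions.

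A reader might go further and infer that the reported response rate is overstated outright. The documents do not support that. The upward direction is certain only against the non-responder convention, which is itself conservative. Against the true rate it depends on how leavers would have fared, which is not known.

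On the documents, the SAP still describes 140 subjects and visits at Weeks 8 and 20, so it precedes the current protocol. Its declaration of no change may have been accurate for the protocol it was written against, which is not available here. Against the current protocol it is not accurate.

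No test, power or sample size is affected.

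**What to change.** 1. Add a Week 26 IGA 0/1 row with the Safety Population as denominator and missing counted as non-response, shown beside the as-observed and LOCF rows. Whether it should be the main summary is a matter of preference.
2. Name Week 26 as the time point for that row. State in the SAP how an early-termination value is assigned, including when it shares a window with a scheduled visit.
3. Reconcile protocol Section 9.1.4.1 with SAP Sections 7.2.5, 7.2.6.2 and 8. Either the protocol admits the LOCF row or the SAP lists it as an addition. The SAP has to be brought into line with the current protocol in any case.

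The cost is one table row and a few sentences, with no new data. The downside is that the added figure is conservative, because a leaver who stayed clear counts as a failure, and it will be less favourable than the as-observed one whenever a responder rate above zero meets any dropout.

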#### **9.1.4.2 *Analyses of the efficacy endpoints***

No formal inferential statistical analysis will be performed. IGA will be summarized by each category and by shift changes over time.

In addition, observed and changes from baseline of the IGA and Pruritus over time will be summarized as continuous variables.

### 9.1.5 Safety analysis methods

No inferential statistical analysis is planned for safety endpoints of the study.

The laboratory parameters at scheduled visits and change from Screening at post-baseline visit(s) will be summarized descriptively by treatment and by visit. A shift table for lab parameters at Screening versus Week 26/ET will be provided when appropriate.

Only Treatment-emergent Adverse Events (TEAEs) will be summarized. A TEAE is defined as an AE with an onset date on or after the first application of the study drug.

TEAEs will be tabulated in frequency tables by System Organ Class and Preferred Term based on the Medical Dictionary for Regulatory Activities (MedDRA). Additional summary tables will be provided for TEAEs that are considered serious (SAEs), related to the study drug(s), and severe. TEAEs that are AESIs, as well as TEAEs leading to discontinuation will also be summarized. For a given TEAE, a subject will be counted once even if he/she has experienced multiple episodes of that particular TEAE. Subgroup summaries of TEAEs will be provided based on gender, age group, and race when appropriate.

Prior and concomitant therapies and procedures will be summarized. A prior therapy/procedure is one that ends at or before baseline; and a concomitant therapy/procedure is one starting after the baseline visit.

Extent of study drug exposure and compliance will also be summarized.

### 9.1.6 Pharmacokinetics analysis

$C_t$  will be submitted after logarithmic transformation (Ln), to paired comparisons of Baseline and each subsequent time point. Ninety percent confidence intervals of the pairwise differences will be calculated using the Student's t statistic. The limits of the intervals will be back-transformed into exponential to obtain 90% confidence intervals of the ratios of geometric means between time points, on the original scale.

PK/PD relationships will be investigated by correlating  $C_t$  with appropriate PD parameters, using Spearman coefficient and graphical illustrations.

